3.3 Study Procedures

Asthmatic patients will be tested at three different times:

- Day 1) ED visit
- Day 2) 48 hours post discharge
- Day 3) 14 days' post discharge

Day 1, participants will be recruited by the Emergency Medicine Research Group (EMeRG). They will receive standard emergency care for their asthma and once stabilized, informed consent will be obtained. A venous blood draw will be done prior to discharge. Once stabilized, the participant will be taken to a private area either within the ED department or [name]

lab in Clinical Sciences Building to ensure no interference with ED procedures. Applanation tonometry will be done to measure PWV, followed by FMD to determine endothelial function. **Day 2** the participant will return and the same assessments as Day 1 will be performed with the addition of spirometry according to standardized guidelines.¹⁸ Medication will not be withheld prior to this assessment. A Fitbit will be given along with instructions to wear the device for 7 days.

Day 3 will consist of the same measurements done in the ED for Day 1, with the addition of 2 quality of life questionnaires, the standardized Asthma Quality of Life Questionnaire (AQLQs) and the EQ-5D (5L), and the Asthma Control Questionnaire (ACQ), finishing with a full pulmonary function test including post-bronchodilator spirometry to evaluate for airway reversibility (i.e. asthma)¹⁹.

The participants are being tested 48 hours following the exacerbation to determine if systemic inflammation is further increased following an exacerbation, or if the exacerbation is when inflammation is at its peak. This will inform us on whether the exacerbation itself is the stimulus for increased systemic inflammation, or if it is a consequence of a stimulus in the days prior. The 14 day follow up was chosen based on the information that CRP is generally recovered to normal values after 14 days following stimulus,²⁰ as well, it is expected that lung function will have recovered 14 days following an exacerbation, as seen in other pulmonary disease exacerbations.²¹ Day 3 will tell us what average values for the participant would most likely be and allow us to compare the values obtained from the exacerbation against a personal reference value.

Stable asthmatics and healthy control participants will be tested at two different times:

- Day 1) date that participant is available for testing
- Day 2) 48 hours after Day 1

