Controls are being tested at two times to determine the degree of natural fluctuations in endothelial function, arterial stiffness, and systemic inflammation in healthy adults.

Measurements

Waist Circumference – Using a fabric tape measure, waist circumference will be measured at the level of the last rib to the nearest 0.1 cm after a normal expiration.¹⁷ This will be used as a measure of adiposity and will potentially be used as a covariate during statistical analysis.

Arterial stiffness - Arterial stiffness will be evaluated using pulse wave velocity (PWV) between the carotid and femoral arteries. After 10 minutes of resting in a dark, quiet room in the supine position, cPWV and pPWV will be recorded using applanation tonometry (Complior, Alam Medical, Saint Quentin Fallavier, France). A series of 10 consecutive beats will be taken with a minimum quality of 85%. The distance between the carotid and femoral artery, as well as the carotid and radial artery will be recorded in mm. PWV will be measured prior to FMD and blood collection, and will be taken on all 3 days of assessments. PWV is expressed as m/s and is calculated as $PWV = L/\Delta t$, with L being the distance between the two points and Δt being the time it takes for the pulse to get from site 1 to site 2.²²

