Systemic inflammation and immune response – Serum CRP, IgE, periostin, YKL-40 and whole blood eosinophils, neutrophils, and IL-17 will be analyzed from venous blood collected at each assessment day at the end of the visit via antecubital venipuncture by a certified phlebotomist following specified guidelines.²⁶ With the participant sitting in a relaxed position, the upper arm will be occluded to increase the accessibility of the blood vessels. Once a vein is chosen (based on proximity to the surface, size, position and absence of scar tissue and/or pulsation), a sterile 25-gauge needle will be inserted at a 30-degree angle or less to initiate blood draw. Blood will be collected in anti-coagulant-free polypropylene tubes pre labeled with the participant's identification number, date and time, and visit number. After two tubes are collected, the tourniquet will be removed followed by the needle and pressure will be applied to the venipuncture site and held until the bleeding stops. Once collected, the blood will be left to clot for a minimum of 30 minutes followed by centrifuging at 1000g for 10 minutes at 4 degrees Celsius. The serum will be separated into aliquots of 75 µg immediately after centrifuging and then stored at -80 degrees Celsius until analysis. Analysis of inflammatory and immune markers will be completed at the University of Alberta.

Physical activity - Physical activity will be evaluated by step count using a Fitbit activity monitor (Fitbit Inc., San Francisco, CA). Participants will be instructed to wear the monitor on their wrist for 7 days, beginning the morning after Day 2 testing. It will only be removed to shower/bathe and to sleep. Total steps in each 24-hour period will be averaged and used to determine activity levels during the first week of recovery. Low active will be defined as <7,500 steps/day. Somewhat active will be defined as 7,500-9,999 steps/day. Active will be defined as > 10,000 steps/day.²⁷

Pulmonary function – all participants will undergo a full pulmonary function test, according to established clinical guidelines.^{19,20} The expiratory volume in 1 second (FEV₁) responses to

4x100 mg Salbutamol will be evaluated, and an increase in FEV₁ of $\geq 12\%$ and 200 ml will be considered positive for significantly reversible airway constriction.²⁸

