3.4.2 Statistical Methods

The mean differences in FMD, systemic inflammation, and arterial stiffness for ED visit compared to the control group will be evaluated using an unpaired t-test. A within-factors repeated measures analysis of variance (ANOVA) will evaluate the mean differences between each assessment day for the exacerbation group to assess change in endothelial function during exacerbation as well as the recovery period. A similar evaluation will be used for arterial stiffness and systemic inflammation/immune response. A one-way analysis of covariance (ANCOVA) will be used to correct for shear rate in FMD for all groups, with both values being reported. An α -level of 0.05 will be used as the significance level for all statistical analysis, and all results will be reported as mean \pm standard deviation unless indicated otherwise.

4 Data Handling and Record Keeping

Data to be collected:

Outcome variables:

Endothelial function

Source of the data: Flow-mediated dilation test (see *measurement, endothelial function* above).

Time point for collection: Collected as the last assessment during the ED visit. For the 2 follow up visits, FMD will be done after arterial stiffness and prior to blood draw.

Who will collect the data: All data will be collected by trained research staff associated with the study.

Why the data is being collected: To evaluate the influence of acute asthma exacerbation on vascular health.

Is the data from a standardized tool: Yes.

What form will the data will take (e.g. binary, continuous (numeric), time to event): Continuous.

Arterial stiffness

Source of the data: pulse wave velocity test (see *measurements, arterial stiffness* above).

Time point for collection: At the ED, arterial stiffness will be collected after blood draw and prior to endothelial function. At the follow up visits, it will be collects as the primary assessment.

Who will collect the data: All data will be collected by trained research staff associated with the study.

Why the data is being collected: To evaluate the influence of acute asthma exacerbation on vascular health.

Is the data from a standardized tool: Yes.

What form will the data will take (e.g. binary, continuous (numeric), time to event): Continuous.

Systemic inflammation and immune response

Source of the data: Venous blood samples (see *measurements, systemic inflammation and immune response* above).

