Time point for collection: At ED, blood will be collected as the primary assessment. At follow up visits, it will be collected as the final assessment.

Who will collect the data: All data will be collected by trained research staff associated with the study.

Why the data is being collected: To evaluate changes in systemic inflammatory levels and immune response throughout the study.

Is the data from a standardized tool: Yes.

What form will the data will take (e.g. binary, continuous (numeric), time to event): Continuous.

Explanatory variables and potential confounding variables:

Participant demographics, health history, and current status

Source of the data: interview with the participant as well as medical chart and ED physician. (see appendix 5)

Time point for collection: in the ED once hemodynamically stable and while receiving treatment. At follow up visits, additional information will be collected prior to assessments.

Who will collect the data: All data will be collected by trained research staff associated with the study.

Why the data is being collected: To ensure subject meet the inclusion/exclusion requirements, to obtain information on potential confounding variables, and to obtain general sample characteristics.

Is the data from a standardized tool: No, demographics will be collected according to the data collection document provided.

What form will the data will take (e.g. binary, continuous (numeric), time to event): Nominal, continuous or ordinal.

Perceived level of control and quality of life

Source of the data: The asthma control questionnaire (see appendix 1), asthma quality of life questionnaire (see appendix 2), and EQ-5D (see appendix 3).

Time point for collection: at 14 day post-discharge follow up.

Who will collect the data: All data will be collected by trained research staff associated with the study.

Why the data is being collected: To evaluate the current levels of perceived asthma control, disease specific quality of life and generalized quality of life.

Is the data from a standardized tool: Yes.

What form will the data will take (e.g. binary, continuous (numeric), time to event): Continuous.

Lung function

Source of the data: Pulmonary function test (see *measurements, pulmonary function* above)

Time point for collection: during a pre-test session, and at each baseline time-point.

Who will collect the data: All data will be collected by trained research staff associated with the study.

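### The plan contradicts itself on when ED blood is drawn; under the Section 4 order, any effect of drawing blood first cannot be separated from the ED visit for FMD and PWV

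*Combined protocol and SAP*

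**What the plan says.** Section 3.3 and Section 4 give different orders for the ED visit.

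- **Section 3.3, arterial stiffness:** "PWV will be measured prior to FMD and blood collection, and will be taken on all 3 days of assessments". Only the exacerbation group has three assessment days, and one of them is the ED visit. This sentence rules out blood before PWV. It does not order FMD against blood.
- **Section 3.3, systemic inflammation:** "venous blood collected at each assessment day at the end of the visit". This is the sentence that places blood last.
- **Section 3.3, Day 1 narrative:** "A venous blood draw will be done prior to discharge". Blood is mentioned before PWV and FMD, but only discharge is set as a limit, so either order fits.
- **Section 3.3, Day 3 narrative:** the visit ends with the full pulmonary function test.
- **Section 4, endothelial function:** "Collected as the last assessment during the ED visit", then "For the 2 follow up visits, FMD will be done after arterial stiffness and prior to blood draw".
- **Section 4, arterial stiffness:** "At the ED, arterial stiffness will be collected after blood draw and prior to endothelial function". At follow-up PWV comes first.
- **Section 4, systemic inflammation:** "At ED, blood will be collected as the primary assessment. At follow up visits, it will be collected as the final assessment".

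PWV precedes FMD in all of these; what changes is the position of blood. Section 4 gives no order for the two control groups. No section names the arm used for FMD or for blood. Tubes are labelled with "identification number, date and time, and visit number".

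**The concern.** Staff working from the measurement text would run a different ED visit from staff working from Section 4. That alone needs correcting.

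The statistical consequence arises if Section 4 is followed. FMD is the primary outcome and PWV a secondary one. Section 3.3 uses the 14-day value as each patient's own reference for the ED value, and Section 3.4.2 compares the ED value with controls. If a preceding venepuncture has any effect on FMD or PWV, that effect is present at every ED visit and absent at every follow-up visit. It falls on the visit that the study exists to examine. Neither planned analysis has an order term, and none could be fitted.

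The markers have the mirror-image problem: ED blood is taken before the 5-minute forearm occlusion and follow-up blood after it.

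There is a further conflict on Day 3. Blood cannot be the final assessment, as Section 4 has it, if the visit finishes with the pulmonary function test, as Section 3.3 has it.

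**Working it through.** The plan gives no figure to reproduce on this point. The check compares the orders and then asks what each contrast estimates.

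**1. Orders side by side**

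- ED visit, Section 3.3 measurement text: PWV, FMD, blood.
- ED visit, Section 4: blood, PWV, FMD.
- Both follow-up visits, either source: PWV, FMD, blood, setting aside where the lung-function tests fall.
- Controls: blood at the end of the visit, if the systemic inflammation paragraph of Section 3.3 is read as covering them; Section 4 is silent.

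**2. Within-person contrasts (repeated-measures ANOVA, Section 3.4.2)**

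Inputs: 36 evaluable patients per group (Section 3.4.1) and three visits (Section 3.1.1). For patient i at visit v, let E mark the ED visit, T the 48-hour visit, and B an FMD taken after study blood:

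y = a_i + b·E + c·T + d·B + error

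Under Section 4, B equals E on every row, so the visit differences estimate:

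- ED minus 14 days: b + d
- ED minus 48 hours: b + d − c
- 48 hours minus 14 days: c

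Only the sum b + d can be estimated. Numerically, 36 patient columns plus 2 visit columns make 38, with rank 38. Adding B makes 39 columns, and the rank stays 38. At the recruited 44 per group, 44 + 2 = 46 columns, and adding B makes 47 with rank still 46. A larger sample does not help. Shear correction does not either: an added covariate cannot break an exact equality between two other columns. It could remove only the part of an order effect that acts through shear.

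As a check on the method, if half the ED patients had blood first and half last, the rank would be 39 of 39 and d would be estimable. The deficit therefore comes from the schedule.

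**3. Between-group contrasts (unpaired t-tests)**

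The rank result covers only the within-person contrasts. For ED versus a control group the argument is direct. With controls blood-last, the mean difference estimates the group difference plus d. With controls blood-first, d is on both sides and cancels, provided it is the same in both groups.

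**4. Contrasts that would carry an order effect, if one exists**

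The five contrasts are ED−48 h, ED−14 d, 48 h−14 d, ED−stable asthma and ED−healthy. Assumption: the single control group named in Section 3.4.2 means each control group in turn.

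- Section 4, controls blood-last: 1, 1, 0, 1, 1, so 4 of 5.
- Section 4, controls blood-first: 1, 1, 0, 0, 0, so 2 of 5.
- PWV, FMD, blood throughout: 0 of 5.
- Blood, PWV, FMD throughout: 0 of 5, if the effect is equal across visits and groups.

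These counts concern the position of blood only. The place of the 48-hour spirometry relative to FMD is not fixed.

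**5. Delay to ED blood if it is drawn last**

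From the times in Section 3.3 (10 minutes supine rest, 5 occlusion, 3 monitoring): 10 + 5 + 3 = 18 minutes if PWV and FMD share one rest, or 10 + 10 + 5 + 3 = 28 if each has its own. Set-up and PWV recording come on top.

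**The case against.** The ED order in Section 4 looks deliberate. Three separate entries agree on it, and the Day 1 narrative mentions blood before the vascular tests. The general sentences in Section 3.3 may simply omit an intended exception, and a short carve-out would remove the contradiction. This stands. It would not remove the non-separability, which would then have to be stated as a limitation.

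Anything constant at the ED visit is aliased with it. Setting, ED treatment and fasting also differ. Appendix 5 lists an IV and a blood panel among ED interventions, so some patients may have had a clinical venepuncture before FMD under any study order. This stands too: a uniform order would not isolate the exacerbation. It removes only what the study's own schedule adds.

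A reader might infer that ED FMD is biased by the blood draw. The documents do not support that. They give no size, direction or mechanism, and the supine rest and the move to a private area may limit any effect. A reader might also infer that the PWV sentence in Section 3.3 by itself places blood last; it does not.

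Appendix 5, as far as it can be read, has no field for the arm or for the clock time of PWV and FMD. Section 4 cites that sheet for demographics, history and current status, so this does not show that these details go unrecorded.

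**Conclusion.** The contradiction is certain, and the ED visit cannot be run as written. If Section 4 governs, the position of blood is completely aliased with the ED visit in the within-person analysis of FMD and PWV, whatever the sample size. In the comparisons with controls this depends on controls having blood last, as the Section 3.3 wording implies. On that reading, four of five contrasts would carry an order effect if there is one; only 48 hours versus 14 days is free of it.

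No magnitude can be attached. This is an avoidable non-separability on the primary outcome, not a demonstrated bias. It should be fixed because the cost is small and the difference is one the study itself creates.

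**What to change.** Bring the visit narratives and the measurement paragraphs of Section 3.3, and the collection-time entries of Section 4 (including lung function), to one order of blood, PWV and FMD. It should hold at every visit and in all three groups, with spirometry and the pulmonary function test after all three. The investigators choose between:

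1. *PWV, then FMD, then study blood, then any lung-function test.* This delays ED blood by at least 18 or 28 minutes, as worked out above. That matters because Section 3.3 makes the timing of peak inflammation a study question.
2. *Study blood, then PWV, then FMD, then any lung-function test, with the 10-minute supine rest kept before PWV and FMD.* This keeps early ED blood, but cancels an order effect only if that effect is equal across visits and groups.

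With either option, record the arm and clock time of blood, PWV and FMD, and of any clinical IV or blood panel. Use the same arm for FMD at all visits and the other arm for study blood where feasible, and record exceptions, since an ED line or poor veins may prevent it.

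If the ED order must stay different, write that exception into the arterial stiffness and systemic inflammation paragraphs of Section 3.3. State as a limitation that the ED contrasts for FMD and PWV include any effect of the prior blood draw. Using the other arm may reduce a local carry-over but does not remove the aliasing.

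The cost is wording in Sections 3.3 and 4 and a few fields on the data form, plus the ED blood delay under option 1.

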4.1 Confidentiality

Each research participant will be assigned a study ID which will not be associated with any personal identifiable information. All collected study data will be stored either on password protected computer hard drives or in locked filing cabinets.

Appendix 1. Asthma Control Questionnaire (used with permission from creator).

**ASTHMA CONTROL
QUESTIONNAIRE (ACQ)**

© 1997
QOL TECHNOLOGIES LTD.

For further information:
[name], MCSP, MSc
Professor
[name]
[name]
[name]
[contact]
[contact]
E-mail: [contact]
Web: <http://www.qoltech.co.uk>

© The Asthma Control Questionnaire (ACQ) is copyrighted and all rights reserved. No part of this questionnaire may be sold, modified or reproduced in any form without the express permission of [name] on behalf of QOL Technologies Limited

DECEMBER 2002

ASTHMA CONTROL QUESTIONNAIRE® PATIENT ID: _____
DATE: _____ Page 1 of 2

Please answer questions 1 - 6.

Circle the number of the response that best describes how you have been during the past week.

- On average, during the past week, how often were you woken by your asthma during the night?
 0 Never
 1 Hardly ever
 2 A few times
 3 Several times
 4 Many times
 5 A great many times
 6 Unable to sleep because of asthma
- On average, during the past week, how bad were your asthma symptoms when you woke up in the morning?
 0 No symptoms
 1 Very mild symptoms
 2 Mild symptoms
 3 Moderate symptoms
 4 Quite severe symptoms
 5 Severe symptoms
 6 Very severe symptoms
- In general, during the past week, how limited were you in your activities because of your asthma?
 0 Not limited at all
 1 Very slightly limited
 2 Slightly limited
 3 Moderately limited
 4 Very limited
 5 Extremely limited
 6 Totally limited
- In general, during the past week, how much shortness of breath did you experience because of your asthma?
 0 None
 1 A very little
 2 A little
 3 A moderate amount
 4 Quite a lot
 5 A great deal
 6 A very great deal

Revised September 2010
ACQ-6A North American English Version

ASTHMA CONTROL QUESTIONNAIRE® PATIENT ID: _____
DATE: _____ Page 2 of 2

- In general, during the past week, how much of the time did you wheeze?
 0 Not at all
 1 Hardly any of the time
 2 A little of the time
 3 A moderate amount of the time
 4 A lot of the time
 5 Most of the time
 6 All the time
- On average, during the past week, how many puffs/inhalations of short-acting bronchodilator (eg. Ventolin/Albuterol) have you used each day?
 (If you are not sure how to answer this question, please ask for help)
 0 None
 1 - 2 puffs/inhalations most days
 2 3 - 4 puffs/inhalations most days
 3 5 - 8 puffs/inhalations most days
 4 9 - 12 puffs/inhalations most days
 5 13 - 16 puffs/inhalations most days
 6 More than 16 puffs/inhalations most days

To be completed by a member of the clinic staff

- FEV₁ pre-bronchodilator: 0 > 90% predicted
 FEV₁ predicted: 1 85 - 90%
 2 75 - 80%
 3 70 - 75%
 FEV₁ % predicted: 4 65 - 70%
 (Record actual values on the dotted lines and score the FEV₁ % predicted in the next column)
 5 60 - 65%
 6 < 50% predicted

Revised September 2010
ACQ-6A North American English Version

Appendix 2. Asthma Quality of Life Questionnaire (used with permission from creator).

ASTHMA QUALITY OF LIFE QUESTIONNAIRE WITH STANDARDISED ACTIVITIES (AQLQ(S))																																																							
SELF-ADMINISTERED																																																							
 
© 1999 GOL TECHNOLOGIES LTD.
																																																							

For further information:
 
[name], MCSP, MSc Professor [name] [contact] [contact] Email: [contact] Web: http://www.poltech.co.uk
				
Development and validation supported by GLAXO WELLCOX, INC.
																																																			

© The Asthma Quality of Life Questionnaire with Standardised Activities (AQLQ(S)) is copyrighted and all rights are reserved. No part of this questionnaire may be sold, modified or reproduced in any form without the express permission of [name] on behalf of GOL Technologies Limited.
																																																							
APRIL 2008																																																							
Modified September 2009																																																							
ASTHMA QUALITY OF LIFE QUESTIONNAIRE (S)				PATIENT ID: _____																																																			
SELF-ADMINISTERED				DATE: _____																																																			
Page 1 of 1																																																							

Please complete all questions by circling the number that best describes how you have been during the last 2 weeks as a result of your asthma.
																																																							

HOW LIMITED HAVE YOU BEEN DURING THE LAST 2 WEEKS IN THESE ACTIVITIES AS A RESULT OF YOUR ASTHMA?
																																																							

  
 	Totally Limited	Extremely Limited	Very Limited	Moderately Limited	Somewhat Limited	A Little Limited	Not Limited	
   
 1. STRENUOUS ACTIVITIES (such as hurrying, exercising, running up stairs, sports)	1	2	3	4	5	6	7	
 
 2. MODERATE ACTIVITIES (such as walking, housework, gardening, shopping, climbing stairs)	1	2	3	4	5	6	7	
 
 3. SOCIAL ACTIVITIES (such as taking, playing with pets/children, visiting friends/relatives)	1	2	3	4	5	6	7	
 
 4. WORK-RELATED ACTIVITIES (tasks you have to do at work) *If you are not employed or self-employed, these should be tasks you have to do most days.	1	2	3	4	5	6	7	
 
 5. SLEEPING	1	2	3	4	5	6	7	
  
									Totally Limited	Extremely Limited	Very Limited	Moderately Limited	Somewhat Limited	A Little Limited	Not Limited	1. STRENUOUS ACTIVITIES (such as hurrying, exercising, running up stairs, sports)	1	2	3	4	5	6	7	2. MODERATE ACTIVITIES (such as walking, housework, gardening, shopping, climbing stairs)	1	2	3	4	5	6	7	3. SOCIAL ACTIVITIES (such as taking, playing with pets/children, visiting friends/relatives)	1	2	3	4	5	6	7	4. WORK-RELATED ACTIVITIES (tasks you have to do at work) *If you are not employed or self-employed, these should be tasks you have to do most days.	1	2	3	4	5	6	7	5. SLEEPING	1	2	3	4	5	6	7
	Totally Limited	Extremely Limited	Very Limited	Moderately Limited	Somewhat Limited	A Little Limited	Not Limited																																																
1. STRENUOUS ACTIVITIES (such as hurrying, exercising, running up stairs, sports)	1	2	3	4	5	6	7																																																
2. MODERATE ACTIVITIES (such as walking, housework, gardening, shopping, climbing stairs)	1	2	3	4	5	6	7																																																
3. SOCIAL ACTIVITIES (such as taking, playing with pets/children, visiting friends/relatives)	1	2	3	4	5	6	7																																																
4. WORK-RELATED ACTIVITIES (tasks you have to do at work) *If you are not employed or self-employed, these should be tasks you have to do most days.	1	2	3	4	5	6	7																																																
5. SLEEPING	1	2	3	4	5	6	7																																																

HOW MUCH DISCOMFORT OR DISTRESS HAVE YOU FELT DURING THE LAST 2 WEEKS?
																																																							

  
 	A Very Great Deal	A Great Deal	A Good Deal	Moderate Amount	Some	Very Little	None	
   
 6. How much discomfort or distress have you felt over the last 2 weeks as a result of CHEST TIGHTNESS?	1	2	3	4	5	6	7	
  
									A Very Great Deal	A Great Deal	A Good Deal	Moderate Amount	Some	Very Little	None	6. How much discomfort or distress have you felt over the last 2 weeks as a result of CHEST TIGHTNESS?	1	2	3	4	5	6	7																																
	A Very Great Deal	A Great Deal	A Good Deal	Moderate Amount	Some	Very Little	None																																																
6. How much discomfort or distress have you felt over the last 2 weeks as a result of CHEST TIGHTNESS?	1	2	3	4	5	6	7																																																

ASTHMA QUALITY OF LIFE QUESTIONNAIRE (S)								PATIENT ID: _____																																																																																																			
SELF-ADMINISTERED								DATE: _____																																																																																																			
Page 2 of 2																																																																																																											

IN GENERAL, HOW MUCH OF THE TIME DURING THE LAST 2 WEEKS DID YOU:
																																																																																																											

  
 	All of the Time	Most of the Time	A Good Bit of the Time	Some of the Time	A Little of the Time	Hardly Any of the Time	None of the Time	
   
 7. Feel CONCERNED ABOUT HAVING ASTHMA?	1	2	3	4	5	6	7	
 
 8. Feel SHORT OF BREATH as a result of your asthma?	1	2	3	4	5	6	7	
 
 9. Experience asthma symptoms as a RESULT OF BEING EXPOSED TO CIGARETTE SMOKE?	1	2	3	4	5	6	7	
 
 10. Experience a WHEEZE in your chest?	1	2	3	4	5	6	7	
 
 11. Feel you had to AVOID A SITUATION OR ENVIRONMENT BECAUSE OF CIGARETTE SMOKE?	1	2	3	4	5	6	7	
  
													All of the Time	Most of the Time	A Good Bit of the Time	Some of the Time	A Little of the Time	Hardly Any of the Time	None of the Time	7. Feel CONCERNED ABOUT HAVING ASTHMA?	1	2	3	4	5	6	7	8. Feel SHORT OF BREATH as a result of your asthma?	1	2	3	4	5	6	7	9. Experience asthma symptoms as a RESULT OF BEING EXPOSED TO CIGARETTE SMOKE?	1	2	3	4	5	6	7	10. Experience a WHEEZE in your chest?	1	2	3	4	5	6	7	11. Feel you had to AVOID A SITUATION OR ENVIRONMENT BECAUSE OF CIGARETTE SMOKE?	1	2	3	4	5	6	7																																																
	All of the Time	Most of the Time	A Good Bit of the Time	Some of the Time	A Little of the Time	Hardly Any of the Time	None of the Time																																																																																																				
7. Feel CONCERNED ABOUT HAVING ASTHMA?	1	2	3	4	5	6	7																																																																																																				
8. Feel SHORT OF BREATH as a result of your asthma?	1	2	3	4	5	6	7																																																																																																				
9. Experience asthma symptoms as a RESULT OF BEING EXPOSED TO CIGARETTE SMOKE?	1	2	3	4	5	6	7																																																																																																				
10. Experience a WHEEZE in your chest?	1	2	3	4	5	6	7																																																																																																				
11. Feel you had to AVOID A SITUATION OR ENVIRONMENT BECAUSE OF CIGARETTE SMOKE?	1	2	3	4	5	6	7																																																																																																				

HOW MUCH DISCOMFORT OR DISTRESS HAVE YOU FELT DURING THE LAST 2 WEEKS?
																																																																																																											

  
 	A Very Great Deal	A Great Deal	A Good Deal	Moderate Amount	Some	Very Little	None	
   
 12. How much discomfort or distress have you felt over the last 2 weeks as a result of COUGHING?	1	2	3	4	5	6	7	
  
													A Very Great Deal	A Great Deal	A Good Deal	Moderate Amount	Some	Very Little	None	12. How much discomfort or distress have you felt over the last 2 weeks as a result of COUGHING?	1	2	3	4	5	6	7																																																																																
	A Very Great Deal	A Great Deal	A Good Deal	Moderate Amount	Some	Very Little	None																																																																																																				
12. How much discomfort or distress have you felt over the last 2 weeks as a result of COUGHING?	1	2	3	4	5	6	7																																																																																																				

IN GENERAL, HOW MUCH OF THE TIME DURING THE LAST 2 WEEKS DID YOU:
																																																																																																											

  
 	All of the Time	Most of the Time	A Good Bit of the Time	Some of the Time	A Little of the Time	Hardly Any of the Time	None of the Time	
   
 13. Feel FRUSTRATED as a result of your asthma?	1	2	3	4	5	6	7	
 
 14. Experience a feeling of CHEST HEAVINESS?	1	2	3	4	5	6	7	
  
													All of the Time	Most of the Time	A Good Bit of the Time	Some of the Time	A Little of the Time	Hardly Any of the Time	None of the Time	13. Feel FRUSTRATED as a result of your asthma?	1	2	3	4	5	6	7	14. Experience a feeling of CHEST HEAVINESS?	1	2	3	4	5	6	7																																																																								
	All of the Time	Most of the Time	A Good Bit of the Time	Some of the Time	A Little of the Time	Hardly Any of the Time	None of the Time																																																																																																				
13. Feel FRUSTRATED as a result of your asthma?	1	2	3	4	5	6	7																																																																																																				
14. Experience a feeling of CHEST HEAVINESS?	1	2	3	4	5	6	7																																																																																																				

ASTHMA QUALITY OF LIFE QUESTIONNAIRE (S)
																																																																																																											

SELF-ADMINISTERED
																																																																																																											
Page 3 of 3																																																																																																											

IN GENERAL, HOW MUCH OF THE TIME DURING THE LAST 2 WEEKS DID YOU:
																																																																																																											

  
 	All of the Time	Most of the Time	A Good Bit of the Time	Some of the Time	A Little of the Time	Hardly Any of the Time	None of the Time	
   
 15. Feel CONCERNED ABOUT THE NEED TO USE MEDICATION for your asthma?	1	2	3	4	5	6	7	
 
 16. Feel the need to CLEAR YOUR THROAT?	1	2	3	4	5	6	7	
 
 17. Experience asthma symptoms as a RESULT OF BEING EXPOSED TO DUST?	1	2	3	4	5	6	7	
 
 18. Experience DIFFICULTY BREATHING OUT as a result of your asthma?	1	2	3	4	5	6	7	
 
 19. Feel you had to AVOID A SITUATION OR ENVIRONMENT BECAUSE OF DUST?	1	2	3	4	5	6	7	
 
 20. WAKE UP IN THE MORNING WITH ASTHMA SYMPTOMS?	1	2	3	4	5	6	7	
 
 21. Feel AFRAID OF NOT HAVING YOUR ASTHMA MEDICATION AVAILABLE?	1	2	3	4	5	6	7	
 
 22. Feel bothered by HEAVY BREATHING?	1	2	3	4	5	6	7	
 
 23. Experience asthma symptoms as a RESULT OF THE WEATHER OR AIR POLLUTION OUTSIDE?	1	2	3	4	5	6	7	
 
 24. Were you WOKEN AT NIGHT by your asthma?	1	2	3	4	5	6	7	
 
 25. AVOID OR LIMIT GOING OUTSIDE BECAUSE OF THE WEATHER OR AIR POLLUTION?	1	2	3	4	5	6	7	
  
													All of the Time	Most of the Time	A Good Bit of the Time	Some of the Time	A Little of the Time	Hardly Any of the Time	None of the Time	15. Feel CONCERNED ABOUT THE NEED TO USE MEDICATION for your asthma?	1	2	3	4	5	6	7	16. Feel the need to CLEAR YOUR THROAT?	1	2	3	4	5	6	7	17. Experience asthma symptoms as a RESULT OF BEING EXPOSED TO DUST?	1	2	3	4	5	6	7	18. Experience DIFFICULTY BREATHING OUT as a result of your asthma?	1	2	3	4	5	6	7	19. Feel you had to AVOID A SITUATION OR ENVIRONMENT BECAUSE OF DUST?	1	2	3	4	5	6	7	20. WAKE UP IN THE MORNING WITH ASTHMA SYMPTOMS?	1	2	3	4	5	6	7	21. Feel AFRAID OF NOT HAVING YOUR ASTHMA MEDICATION AVAILABLE?	1	2	3	4	5	6	7	22. Feel bothered by HEAVY BREATHING?	1	2	3	4	5	6	7	23. Experience asthma symptoms as a RESULT OF THE WEATHER OR AIR POLLUTION OUTSIDE?	1	2	3	4	5	6	7	24. Were you WOKEN AT NIGHT by your asthma?	1	2	3	4	5	6	7	25. AVOID OR LIMIT GOING OUTSIDE BECAUSE OF THE WEATHER OR AIR POLLUTION?	1	2	3	4	5	6	7
	All of the Time	Most of the Time	A Good Bit of the Time	Some of the Time	A Little of the Time	Hardly Any of the Time	None of the Time																																																																																																				
15. Feel CONCERNED ABOUT THE NEED TO USE MEDICATION for your asthma?	1	2	3	4	5	6	7																																																																																																				
16. Feel the need to CLEAR YOUR THROAT?	1	2	3	4	5	6	7																																																																																																				
17. Experience asthma symptoms as a RESULT OF BEING EXPOSED TO DUST?	1	2	3	4	5	6	7																																																																																																				
18. Experience DIFFICULTY BREATHING OUT as a result of your asthma?	1	2	3	4	5	6	7																																																																																																				
19. Feel you had to AVOID A SITUATION OR ENVIRONMENT BECAUSE OF DUST?	1	2	3	4	5	6	7																																																																																																				
20. WAKE UP IN THE MORNING WITH ASTHMA SYMPTOMS?	1	2	3	4	5	6	7																																																																																																				
21. Feel AFRAID OF NOT HAVING YOUR ASTHMA MEDICATION AVAILABLE?	1	2	3	4	5	6	7																																																																																																				
22. Feel bothered by HEAVY BREATHING?	1	2	3	4	5	6	7																																																																																																				
23. Experience asthma symptoms as a RESULT OF THE WEATHER OR AIR POLLUTION OUTSIDE?	1	2	3	4	5	6	7																																																																																																				
24. Were you WOKEN AT NIGHT by your asthma?	1	2	3	4	5	6	7																																																																																																				
25. AVOID OR LIMIT GOING OUTSIDE BECAUSE OF THE WEATHER OR AIR POLLUTION?	1	2	3	4	5	6	7																																																																																																				

ASTHMA QUALITY OF LIFE QUESTIONNAIRE (S)		PATIENT ID: _____						
SELF-ADMINISTERED		DATE: _____						
Page 4 of 5								
IN GENERAL, HOW MUCH OF THE TIME DURING THE LAST 2 WEEKS DO YOU:								
	Not at All Day Time	Not at All the Time	A Good Bit of the Time	Some of the Time	A Little of the Time	Mostly All of the Time	Most of the Time	
